### **9.7.4 Patient's Participation Stopping Criteria**

In the opinion of the Investigator, if the patient suffers an AE that warrants discontinuation of the study drug because of interference with age-appropriate instrumental ADL (Activities of Daily Living), for example preparing for meal, shopping for groceries or clothing, using the telephone, etc. the patient will be followed until the AE resolves or is considered stable. Any subject that discontinues the study because of an adverse event will be followed until resolution or stabilization of the adverse event.

## **9.8 Serious Adverse Events**

### **9.8.1 Definition of a Serious Adverse Event**

A Serious Adverse Event (SAE) is any untoward medical occurrence that at any dose suggests a medically significant hazard, including any event that:

- Results in death – includes all deaths, even those that appear to be completely unrelated to study treatment (e.g., car accident where patient is a passenger).
- Is life-threatening – in the view of the Investigator, the patient is at immediate risk of death at the time of the event.
- Results in persistent or significant disability or incapacity (substantial disruption of one's ability to conduct normal life).
- Requires inpatient hospitalization or prolongation of existing hospitalization.
- Causes congenital anomaly or birth defect.
- Is an important medical event that may not be immediately life-threatening or result in death or hospitalization, but may jeopardize the patient or may require medical or surgical intervention to prevent one of the serious outcomes listed above (e.g., intensive treatment in an emergency room, convulsions that do not result in hospitalizations). Emergency Room visits that require medical or surgical

## **CONFIDENTIAL PROTOCOL**

A Randomized, Double-Blind, Placebo-Controlled, Parallel-Design, Multiple-Site Clinical Study to Evaluate the Efficacy and Safety of Desoximetasone Topical Spray, 0.15% (Taro Pharmaceuticals, U.S.A., Inc.) in Patients with Mild to Moderate Plaque Psoriasis

---

intervention to prevent one of the other serious outcomes listed above are considered a Serious Adverse Event.

### **9.8.2 Reporting Serious Adverse Events**

#### Investigator Reporting of SAEs

Adverse events which are evaluated by the Investigator as "Serious" will be reported to the Sponsor and IRB within 24 hours of notice whether or not they are considered expected or drug-related. All SAEs will be reported as per applicable regulations. All SAEs encountered during the study will be reported on the appropriate form and summarized in the final report.

**Any serious or unexpected adverse events should be reported to Novum within 24 hours. Following is the contact information:**

[name]  
Vice President, Clinical Trials  
[contact]  
[contact] [name]  
[contact]

Or

[name] [name]  
Medical Monitor  
[name]  
[contact] [name]  
[contact]

Novum will report any Serious Adverse Event to Taro.

Documentation should be sent to Taro's Study Manager and/or Taro's Drug Safety Department listed below:

Taro Study Manager:  
[name]  
Coordinator, Clinical Operation  
[contact] [name]  
Email: [[contact]](mailto:[contact])

Taro Drug Safety Manager:  
[name] [name], BSN,  
Drug Safety Manager, Medical Affairs  
[contact] [name]  
Email: [[contact]](mailto:[contact])  
and [[contact]](mailto:[contact])

Investigators will be informed of any SAEs reported at other study sites within 15 days from the initial report.

## **CONFIDENTIAL PROTOCOL**

A Randomized, Double-Blind, Placebo-Controlled, Parallel-Design, Multiple-Site Clinical Study to Evaluate the Efficacy and Safety of Desoximetasone Topical Spray, 0.15% (Taro Pharmaceuticals, U.S.A., Inc.) in Patients with Mild to Moderate Plaque Psoriasis

---

### **10.0 STATISTICAL METHODS**

#### **10.1 Statistical Plan**

A Statistical Analysis Plan (SAP), detailing the intended statistical analysis of the study data, will be prepared as a separate document and finalized before database lock. Any deviation from the original statistical plan will be described and justified in the final report, as appropriate. The procedure for accounting for missing, unused and spurious data will be included in the Statistical Analysis Plan.

All statistical analysis will be conducted using SAS®, Version 9.4 or higher.

#### **10.2 Determination of Sample Size**

The primary analyses of interest are the proportion of patients in the Test and Vehicle treatment groups who are considered to be a Clinical Success and Treatment Success on Day 28.

In-house data from two Phase III studies that evaluated the safety and efficacy of desoximetasone spray 0.25% (twice daily for 28 days) in patients with moderate to severe plaque psoriasis were used for sample size determination. These studies were conducted in support of Taro's NDA #204141, Topicort® (desoximetasone) Topical Spray, 0.25%. In those studies the Clinical Success rates were 31% and 53% for the active product (42% average) and 5% and 18% for the vehicle treatment (12% average), and the Treatment Success rates were 39% and 53% for the active product (46% average) and 7% and 17% for the vehicle treatment (12% average).

Based on the average results from these two studies on the 0.25% spray, the proportion of subjects in the Test group considered a Clinical Success and Treatment Success is expected be 40% or higher and the proportion of subjects in the Vehicle group considered a Clinical Success and Treatment Success is expected to be 12% or less for desoximetasone spray 0.15% in patients with mild to moderate plaque psoriasis. With these assumptions, 50 evaluable subjects in the ITT in each treatment group will demonstrate superiority of the Test to the Vehicle group with 89% power at the 5% level of significance ( $p < 0.05$ , using two-sided Z-test), assuming 100% correlation between Clinical and Treatment Success rates.

To allow for patients who may drop out from the study or are otherwise non-evaluable, up to 120 patients may be enrolled (60 in the Test group and 60 in the Vehicle group).

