Sample Size Determination	
The primary analyses of interest are the proportion of patients in the Test and Vehicle treatment groups who are considered to be a Clinical Success and Treatment Success on Day 28.
 
In-house data from two Phase III studies that evaluated the safety and efficacy of desoximetasone spray 0.25% (twice daily for 28 days) in patients with moderate to severe plaque psoriasis were used for sample size determination. These studies were conducted in support of Taro's NDA #204141, Topicort® (desoximetasone) Topical Spray, 0.25%. In those studies the Clinical Success rates were 31% and 53% for the active product (42% average) and 5% and 18% for the vehicle treatment (12% average), and the Treatment Success rates were 39% and 53% for the active product (46% average) and 7% and 17% for the vehicle treatment (12% average).
 
Based on the average results from these two studies on the 0.25% spray, the proportion of subjects in the Test group considered a Clinical Success and Treatment Success is expected be 40% or higher and the proportion of subjects in the Vehicle group considered a Clinical Success and Treatment Success is expected to be 12% or less for desoximetasone spray 0.15% in patients with mild to moderate plaque psoriasis. With these assumptions, 50 evaluable subjects in the ITT in each treatment group will demonstrate superiority of the Test to the Vehicle group with 89% power at the 5% level of significance (<math>p < 0.05</math>, using two-sided Z-test), assuming 100% correlation between Clinical and Treatment Success rates.
 
To allow for patients who may drop out from the study or are otherwise non-evaluable, up to 120 patients may be enrolled (60 in the Test group and 60 in the Vehicle group).

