## CONFIDENTIAL PROTOCOL

A Randomized, Double-Blind, Placebo-Controlled, Parallel-Design, Multiple-Site Clinical Study to Evaluate the Efficacy and Safety of Desoximetasone Topical Spray, 0.15% (Taro Pharmaceuticals, U.S.A., Inc.) in Patients with Mild to Moderate Plaque Psoriasis

---

for the treatment of plaque psoriasis. Topical application of high potency steroids at the recommended dosing levels are usually well tolerated in all populations, with less than 2% of patients reporting adverse reactions (7% in the pediatric population). The most commonly reported adverse events are burning, stinging, pruritus, and skin thinning/atrophy.

The design for this study is based on results from Phase II dose-ranging and Phase III efficacy studies (NDA # 204141) conducted for Topicort® (desoximetasone) 0.25% topical spray (Taro Pharmaceuticals U.S.A., Inc.). The primary efficacy endpoints (Clinical Success and Treatment Success) are based on these studies as well as those reported in the NDA (# 021835) for the marketed product, Clobex® (clobetasol) 0.05% spray. A sample size estimation of 120 enrolled patients (60 patients per treatment group, 1:1 ratio) is based on the assumption that  $\geq 40\%$  of patients receiving Test (active) treatment, and  $\leq 12\%$  of patients receiving Placebo (vehicle) treatment will have Clinical Success and Treatment Success.

Statistical analyses of the clinical data will be based on FDA guidances and any communications with FDA on how they would like such data analyzed.

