### **10.6 Primary Efficacy Analyses**

The Test treatment will be compared with Placebo for each primary endpoint at the 5% significance level ( $p < 0.05$ ; two-sided, Cochran-Mantel-Haenszel exact test) in the ITT population using last observation carried forward (LOCF). Superiority of Test over Placebo will be demonstrated if both dichotomous endpoints show statistical significance at the 5% significance level.

For sensitivity testing, the primary analysis will also be performed using the PP population.

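### The 89% power in section 10.2 is for a Z-test with perfectly correlated endpoints; under the section 10.6 rule, 50 per group gives at most 87%, and 76% if the endpoints are independent

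*Protocol*

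**What the plan says.** Section 10.2, repeated under Sample Size Determination in the synopsis, expects at least 40% success on Test and at most 12% on Vehicle for both Clinical Success and Treatment Success. From this it concludes that "50 evaluable subjects in the ITT in each treatment group will demonstrate superiority of the Test to the Vehicle group with 89% power" at the two-sided 5% level. The stated method is a Z-test, "assuming 100% correlation between Clinical and Treatment Success rates". It then adds: "To allow for patients who may drop out from the study or are otherwise non-evaluable, up to 120 patients may be enrolled", that is, 60 per group.

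Section 10.6 specifies a "two-sided, Cochran-Mantel-Haenszel exact test" for each primary endpoint in the ITT population with LOCF. The decision rule follows: "Superiority of Test over Placebo will be demonstrated if both dichotomous endpoints show statistical significance at the 5% significance level". The synopsis repeats it.

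Section 10.3.1 defines the ITT as every randomized subject, and sections 9.3.5 and 10.3.1 keep patients who stop early in it through LOCF. Section 7.3 attaches the same 40% and 12% assumptions to 60 per group: "A sample size estimation of 120 enrolled patients (60 patients per treatment group, 1:1 ratio) is based on the assumption that" these rates hold.

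**The concern.** The power sentence and the decision rule describe two different procedures. An exact test is more conservative than a Z-test at these sample sizes. Requiring significance on both endpoints lowers power unless the two endpoints always agree within a patient. A correlation of 100% is the single value at which the both-endpoints rule costs nothing, so the calculation rests on the most favourable case, without data to support it.

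The population wording adds a second difficulty. If the ITT is everyone randomized, drop-outs cannot reduce it from 60 to 50, and the reader cannot tell which number the power refers to.

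At stake is the risk of missing a true effect. An 89% power implies an 11% chance of failure. If the real figure is lower, the sponsor has accepted more risk than the document states.

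**Working it through.** **Inputs.** Success rates 40% and 12% for both endpoints, two-sided 5% level, 50 evaluable per group, ceiling of 60 per group (section 10.2); exact test and both endpoints required (section 10.6). The within-patient correlation φ between the endpoints is not given, so 0 to 1 is taken as an assumed range.

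**1. The plan's own figure.** Pooled Z-test, n = 50 per group, difference d = 0.40 − 0.12 = 0.28, mean rate 0.26:

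- SE under no difference: √(2 × 0.26 × 0.74 / 50) = 0.0877
- SE under the alternative: √((0.40 × 0.60 + 0.12 × 0.88) / 50) = 0.0831
- Power = Φ((0.28 − 1.96 × 0.0877) / 0.0831) = Φ(1.30) = 90.3%

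This is close to 89%, so the figure is not a miscalculation on its own terms. It is single-endpoint power, which equals both-endpoints power only at φ = 1.

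**2. Effect of the exact test alone.** The protocol names no CMH strata, so an unstratified two-sided Fisher test is the stand-in. Summing both binomial distributions over all outcomes with p < 0.05 in favour of Test gives, for one endpoint, 87.2% at 50 per group and 92.6% at 60.

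**3. Effect of requiring both endpoints.** In each group the probability that a patient succeeds on both endpoints is p₁₁ = p² + φp(1 − p). At φ = 0.5 this is 0.16 + 0.5 × 0.24 = 0.28 on Test and 0.0144 + 0.5 × 0.1056 = 0.0672 on Vehicle. Joint power is the total probability, over the bivariate binomial in each group, of outcomes where both Fisher tests reject in favour of Test. At φ = 0 it is the square of the single-endpoint power: 0.8721² = 0.761 at 50 and 0.9262² = 0.858 at 60.

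| n per group | φ = 0 | 0.5 | 0.8 | 0.9 | 1 |
|---|---|---|---|---|---|
| 50 | 76.1% | 79.1% | 82.0% | 83.6% | 87.2% |
| 55 | 81.4% | 83.6% | 86.0% | 87.2% | 90.2% |
| 60 | 85.8% | 87.4% | 89.2% | 90.2% | 92.6% |

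The smallest n per group that reaches 89% is 53 at φ = 1, 60 at 0.8, 62 at 0.5 and 64 at 0.

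**4. Stratification by site.** A site-stratified exact CMH test was simulated with equal sites and the same rates in each (40,000 trials per setting, Monte Carlo SE at most 0.22 points). For φ = 0 / 0.5 / 0.8 / 1 it gives 75.3 / 78.6 / 81.5 / 87.1% at 50 per group with 5 sites, and 86.2 / 87.9 / 89.5 / 93.1% at 60 per group with 10 sites. The stand-in does not drive the result.

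**5. The cited Phase III rates.** At 50 per group, exact test, both endpoints required, from φ = 0 to the largest correlation the rates allow:

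- 31%/39% versus 5%/7%: 89.1% to 91.2%
- 53%/53% versus 18%/17%: 90.8% to 94.7%
- averages 42%/46% versus 12%/12%: 87.5% to 91.1%

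These marginal rates do not reveal φ, and they set no upper limit on it at the equal planning rates.

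**The case against.** The strongest reply is that the protocol discloses its method and its correlation assumption, and under them the figure reproduces. That stands: this is a mismatch between planning and analysis, not a slip in the sum.

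The exact test by itself costs under 2 points against the stated figure (87.2% versus 89%). Most of the possible shortfall comes from the correlation. Independence is unlikely here, since both endpoints are scored by the Investigator at the same visit from erythema, scaling and plaque elevation. That also stands. Over φ = 0.5 to 0.9, a more realistic range, power at 50 per group is about 79% to 84%. Even so, a high correlation of 0.9 leaves it more than 5 points below the claim.

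An all-randomized ITT could hold 60 per group, where power is 86% to 93%, and the planning rates are worded as bounds (at least 40%, at most 12%). Both points limit the consequence. They do not repair the sentence, which names 50 per group, and enrolment to 120 is a ceiling rather than a commitment.

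Finally, the 60-per-group figures assume that patients carried forward by LOCF succeed at the same 40% and 12%. As an assumed extreme, if the 10 extra patients per group all count as failures, the rates become 20/60 = 33.3% and 6/60 = 10%, and joint power is about 71% (φ = 0) to 84% (φ = 1). This is a fair qualification and belongs in any restated text.

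**Conclusion.** The concern holds. At the plan's own 40% versus 12% and 50 per group, the section 10.6 rule does not deliver 89% power at any correlation. The chance of missing the effect is about 13% to 24%, against the 11% implied.

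The shortfall is confined to the stated 50 per group at those rates. At 60 per group power is 86% to 93% and reaches 89% at a correlation of about 0.8; at the cited Phase III rates it is about 87% to 95% even at 50. The conclusion rests on Fisher's test as stand-in for the exact CMH test, the same correlation in both groups, and 40% and 12% holding in the analysed ITT. Separately, the evaluable-patient count and the drop-out allowance do not fit an ITT of all randomized patients with LOCF.

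**What to change.** In section 10.2 and the synopsis, replace the 89% sentence with the joint power of the planned exact test for both endpoints, with the correlation labelled as an assumption and shown over its range. At 40% versus 12% and correlation 0, 0.5 and 1, this is about 86%, 87% and 93% with 60 randomized per group, and about 76%, 79% and 87% with 50. State that these figures assume the 40% and 12% apply to all randomized patients, including those carried forward by LOCF.

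Reword the count of evaluable patients and the drop-out sentence so that they match sections 9.3.5 and 10.3.1, and make clear which number per group the power refers to.

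The cost is edited text in two places and a less favourable figure at 50 per group. No change to enrolment, test or decision rule is needed.

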#### **10.3 Study Populations**

##### **10.3.1 Intent-to-Treat (ITT) Population**

The ITT population will include:

- All randomized subjects.

Patients discontinued early for any reason will be included in the ITT with their Last Observation Carried Forward (LOCF).

## **CONFIDENTIAL PROTOCOL**

A Randomized, Double-Blind, Placebo-Controlled, Parallel-Design, Multiple-Site Clinical Study to Evaluate the Efficacy and Safety of Desoximetasone Topical Spray, 0.15% (Taro Pharmaceuticals, U.S.A., Inc.) in Patients with Mild to Moderate Plaque Psoriasis

---

### **10.3.2 Per-Protocol (PP) Population**

The PP population is a sub-population of the ITT population and will include:

- Patients who met all inclusion and exclusion criteria and were randomized according to the randomized treatment assignment.
- Patients who applied at least one dose AND had at least one post-baseline evaluation.
- Patients who were compliant with the dosage regimens following randomization.
- Patients who had no major protocol deviations.

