### 9.3.5 Early Terminations

If a patient terminates from the study early, all efforts will be made to complete Visit 4 study procedures. In case of early termination the Investigator shall fully document the reason for early termination.

Patients who discontinue early or who significantly deviate from the protocol will be included in the intent-to-treat (ITT) population with LOCF.

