## 9.4 Treatments

The following treatments will be used in the study:

- **Test:** Desoximetasone topical spray, 0.15% (Taro Pharmaceuticals, U.S.A., Inc.), applied twice a day for 28 days
- **Placebo:** Vehicle spray (Taro Pharmaceuticals, U.S.A., Inc.) applied twice a day for 28 days

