### 9.4.5 Compliance

Patients will be provided with a diary to record the time and date of dosing, other concomitant medications and adverse events. Patients taking fewer than 75% or more than 125% of the required doses, or who missed scheduled applications for > 3 consecutive days will be considered non-compliant with dosing. Compliance with dosing will be verified by the use of the patient diaries.

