### **9.6.11 Dosing Compliance**

Dosing compliance will be checked by site staff at Visits 2, 3 and 4 by reviewing patient diary entries. Patients will be considered compliant with dosing if they administer 75%-125% of the required number of doses, and did not miss more than 3 consecutive days of dosing.

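### The Per-Protocol criteria do not tie membership to a Visit 4 score within Day 28 ± 2, where both co-primary endpoints are measured

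*Protocol*

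**What the plan says.** Protocol 10.5 defines Clinical Success (IGA) and Treatment Success (TLSS) at Day 28 ± 2, the window of Visit 4. Section 10.6 tests both in the ITT population with LOCF and adds: "For sensitivity testing, the primary analysis will also be performed using the PP population". The protocol names no other sensitivity analysis.

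Section 10.3.2 sets four criteria for the PP set, to be met together:

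- eligibility and randomisation as assigned;
- on exposure and evaluation: "Patients who applied at least one dose AND had at least one post-baseline evaluation";
- on adherence to dosing, a separate line: "Patients who were compliant with the dosage regimens following randomization";
- on conduct, the absence of any major deviation, a term the protocol does not define.

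Compliance is defined in two places. Section 9.4.5 treats as non-compliant "Patients taking fewer than 75% or more than 125% of the required doses, or who missed scheduled applications for > 3 consecutive days". Section 9.6.11 gives the same rule in positive form: "Patients will be considered compliant with dosing if they administer 75%-125% of the required number of doses", together with the same limit on consecutive missed days. Treatment is "applied twice a day for 28 days" (9.4). On early leavers, 9.3.5 says: "Patients who discontinue early or who significantly deviate from the protocol will be included in the intent-to-treat (ITT) population with LOCF". It also asks sites to try to carry out the Visit 4 procedures at early exit.

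**The concern.** A PP analysis of a Day 28 endpoint should describe patients who were treated and measured as planned at Day 28. Section 10.3.2 does contain an evaluation requirement, so this is not a detail simply left for later. The requirement is set at one post-baseline evaluation of any kind, and a Day 7 or Day 14 visit satisfies it. If an in-window Visit 4 were already demanded by another criterion, this one would do no work.

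What is at stake is interpretation. Section 10.6 repeats the primary analysis, which uses LOCF, in the PP set and does not say that LOCF is dropped there. To the extent that the PP set holds the same carried-forward or off-schedule scores as the ITT set, agreement between the two says little about missed or mistimed final visits.

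**Working it through.** **Inputs.** Twice daily for 28 days (9.4). Compliance is 75%–125% of required doses with no more than 3 consecutive days missed (9.4.5, 9.6.11). Visits at Day 7, 14 and 28, each ± 2. Planning values in 10.2: 40% against 12%, 50 evaluable per group, two-sided 5% Z-test, stated power 89%.

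**Step 1: the plan's own figure.** With n = 50 and mean rate 0.26, the pooled-variance Z-test gives Φ[(0.28 − 1.96 × √(2 × 0.26 × 0.74/50)) / √((0.40 × 0.60 + 0.12 × 0.88)/50)] = Φ[(0.28 − 0.172)/0.083] = 90.3%. This reproduces the stated 89% to within about a point. Fisher's exact test gives 87.2%.

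**Step 2: compliance counted against all planned doses.** Required doses = 2 × 28 = 56; the 75% floor is 0.75 × 56 = 42 doses, or 21 full days. Both parts of the rule must hold:

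| Last dosing day | Share of 56 doses | Consecutive days missed to Day 28 | Compliant? |
|---|---|---|---|
| 7 | 25% | 21 | no |
| 14 | 50% | 14 | no |
| 21 | 75% | 7 | no |
| 24 | 86% | 4 | no |
| 25 | 89% | 3 | yes |
| 28 | 100% | 0 | yes |

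Dosing must therefore reach about Day 25. Two routes into the PP set remain:

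- A patient doses to Day 25–28 and misses Visit 4. The last score is from Visit 3 (Day 14), and LOCF would carry it forward.
- A patient has the Visit 4 procedures outside Days 26–30, for example at an early exit on Day 25 or at a late visit.

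A Day 7 score is unlikely to enter on this reading. Visit 3, when the second bottle is dispensed, would also have to be missed. One 100 ml bottle at the stated maximum of 6 ml a day lasts 100/6 = 16.7 days. Reaching Day 25 on it would mean using no more than 100/25 = 4 ml a day.

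**Step 3: compliance counted only up to discontinuation.** The protocol does not say which count applies, and 9.6.11 has compliance checked at Visits 2, 3 and 4. On a to-date count, a patient who stops at Day 7 having taken 14 of 14 doses is 100% compliant, and so is one who stops at Day 14 with 28 of 28. Both then meet the evaluation criterion as well.

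**Step 4: size.** The documents give no early success rates, so these are assumed. Let a share s of a 50-per-group set carry an early score, with success at a fraction f (0 to 0.5) of the Day 28 rate in both groups. Then Test = 0.40 × (1 − s + f·s) and Vehicle = 0.12 × (1 − s + f·s). Power uses the Step 1 formula.

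| s | f | Test vs Vehicle | Difference (points) | Power |
|---|---|---|---|---|
| 0 | – | 40.0% vs 12.0% | 28.0 | 90.3% |
| 5% | 0 | 38.0% vs 11.4% | 26.6 | 88.1% |
| 5% | 0.5 | 39.0% vs 11.7% | 27.3 | 89.3% |
| 10% | 0 | 36.0% vs 10.8% | 25.2 | 85.6% |
| 10% | 0.5 | 38.0% vs 11.4% | 26.6 | 88.1% |
| 20% | 0 | 32.0% vs 9.6% | 22.4 | 79.7% |
| 20% | 0.5 | 36.0% vs 10.8% | 25.2 | 85.6% |

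**The case against.** The strongest reply is that the criteria work together and mostly do the job. A reader might infer that anyone with a single post-baseline visit is in the PP set. That is not so: compliance and the absence of a major deviation are also required. A reader might also infer from the 75% floor that a patient leaving at Day 21 qualifies. Against 56 doses that patient fails, because seven consecutive days are missed. The 56-dose count is arguably the natural one, since 10.3.2 speaks of compliance with the dosage regimen and the regimen is 28 days. These points stand, and they confine the problem on that reading to the end of treatment.

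Two further points are fair in part. A missed or badly late Visit 4 could be classed as a major deviation, and 10.1 leaves missing-data handling to the SAP, which was not available for this review. That may close the gap in practice, but nothing in the protocol makes either event a major deviation, and the stated evaluation threshold would still be too low. Next, LOCF is tied in the text to the ITT population, and 10.6 does not say expressly that it applies in the PP set. If it does not, a patient who misses Visit 4 is in the PP set with no endpoint value, which the same correction would settle.

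Section 9.3.5 might be read as keeping early leavers out of the PP set. It only places them in the ITT population and does not mention the PP set, so it neither closes the gap nor contradicts 10.3.2.

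**Conclusion.** The point holds in limited form. The PP criteria do not tie membership to a Visit 4 assessment within Day 28 ± 2, and neither the compliance rule nor the undefined term for major deviations clearly supplies that tie. Counted against 56 doses, what gets through is a near-full-course patient with a Day 14 score or an out-of-window Visit 4. Entry of Day 7 and Day 14 leavers depends on the other, unstated, dose count and should not be asserted as what the plan does.

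The effect is modest. At a 5%–10% share of early scores, the difference loses about 1 to 3 points and power about 1 to 5 points. The 20% row is an upper illustration, unlikely on the 56-dose reading. Those figures rest on assumed early success rates and on n = 50 per group, borrowed from the ITT planning; out-of-window scores were not modelled. The main loss is in how informative the sensitivity analysis is. A reader might infer that the primary result is at risk. It is not: the ITT analysis and the sample size do not depend on the PP definition. The correction is worth making because it is cheap and concerns the only sensitivity analysis the protocol names.

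**What to change.** In 10.3.2, and in the SAP to match:

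1. Replace the one-evaluation requirement with *a Visit 4 IGA and TLSS evaluation within Day 28 ± 2*. Visit 4 procedures done at an early exit would then count only if they fall in that window.
2. Keep patients discontinued for insufficient therapeutic response in the PP set as failures, in line with the failure definitions in 10.5. Without this exception, the new requirement would drop clear failures from the set.
3. State that compliance for all other patients is computed against the doses scheduled up to Visit 4, and use the same denominator in 9.4.5 and 9.6.11.

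The cost is a few sentences and a slightly smaller PP set. The ITT primary analysis and the sample size are unchanged.
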